9.2 Partial dates

Partial dates are not expected for start and end dates of adverse events. Queries will be raised and resolved in case of partial dates in AE prior to database lock.

Partial dates may be imputed for medications and diseases to determine whether they are concomitant medications or concurrent diseases using the algorithm given below.

For medical history, end dates will be imputed as follows:

- If marked “ongoing” with no end date, then this will be considered as concurrent disease.
- If only year is present, then impute date and month as 31-DEC.
- If month and year are present, then impute date with last date of the month.
- If date and year are present, then impute month as DEC.
- If year is missing, then impute subject’s last visit date in the study.

If the imputed end date is later than subject’s last visit date, then the subject’s last visit date will be imputed. In case of ambiguity, then the worst case is considered (that is, concurrent diseases) for safety analyses.

Example,

Partial End Date	Imputed End Date
--JUN2019	30JUN2019
----2019	31DEC2019
12---2018	12DEC2018
14MAR----	Subject's last visit date

For concomitant medications, start dates will be imputed as follows:

- If only year is present, then impute date and month as 01-JAN.
- If month and year are present, then impute date with first date of the month.
- If date and year are present, then impute month as month as JAN.
- If year is missing, then impute subject’s first IMP date in the study.

If the imputed start date is earlier than subject's first IMP date, then the subject's first IMP date will be imputed. In case of ambiguity, then the worst case is considered (that is, concomitant medications) for safety analyses.

Example,

Partial Start Date	Imputed Start Date
--JUN2019	01JUN2019
-----2019	01JAN2019
12---2018	12JAN2018
14MAR----	Subject's first IMP date

Imputed dates will be used for analyses and collected dates will be recorded in database will be displayed in listings.

9.3 Handling Outliers

Safety and Efficacy endpoints will be cleaned and reviewed periodically during the course of the study. There are no outliers expected during database lock. In exceptional cases, the handling conditions for these will be discussed during the blinded review meeting prior to DBL.

9.4 Blinded Review Meeting

- Exclusion of subjects from each of the population definitions defined in Section 10 will be reviewed and finalized.
- Protocol deviation classifications will be reviewed and finalized.
- Any repeat assessments for safety and efficacy endpoints, and its inclusion in summaries will be finalized.
- Conversion factors for laboratory parameters to SI units will be confirmed.
- Any subjects who did not take treatment as planned will be reviewed.
- Timing of replacement subjects to be reviewed after discontinuation of original subjects.
- Any self-evident corrections in spelling of free text values will be confirmed.
- Incorrect derivations in EDC derived values to be verified.
- Changes from planned analyses / extent of exploratory or additional analyses will be finalized.
- Any outlier values identified during pre-final data review will be closed.

10 Analysis Sets

The membership of the analysis sets will be reviewed and finalized during the blinded review of the data conducted prior to database lock.

10.1 Screened Analysis Set

The Screened Analysis Set includes all subjects who gave informed consent.

The Screened Analysis Set will be used for summary of subject disposition. There will not be any treatment wise analysis when using the Screened Analysis Set.

10.2 All-enrolled Analysis Set

The All-enrolled Analysis Set includes all subjects who gave informed consent and enrolled in the trial. The All-enrolled set will be used to list all screened subjects.

The all-enrolled analysis set will be used for summary of subject disposition. There will not be any treatment wise analysis when using the all-enrolled analysis set.

10.3 Randomized Analysis Set

The Randomized Analysis Set includes all subjects who passed eligibility criteria and were randomized.

The Randomized Analysis Set will be used for summaries of subject disposition, demographics, baseline characteristics and protocol deviations. Subjects will be analyzed according to the treatment group they were assigned at randomization.

Note: If a subject is randomized but did not take the study drug, then the subject will be included only in the Screened, All-Enrolled and Randomized Analysis Sets. Subjects with negative COVID RT-PCR results post randomization will still be included.

10.4 Full Analysis Set

All subjects given ≥ 1 dose of study drug will be included in the Full Analysis Set (FAS) according to actual drug received.

The FAS is the primary analysis set to analyze all efficacy endpoints. Subject disposition, demographic and baseline characteristics of the FAS will also be presented. Subjects will be analyzed according to the treatment group they actually received. Differences between planned and actual treatment, if any, will be discussed during the blinded review meeting.

Note: if a subject had inadvertently taken the study drug without randomization and/or had negative COVID RT-PCR results post study drug administration, the subject would still be included in the Full analysis set.

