## **11.3. Analysis Populations**

The Full Analysis Set (FAS) will include subjects given ≥ 1 dose of study drug according to actual drug received.

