10.5 Safety Analysis Set

The Safety Analysis Set includes all subjects who received at least one dose of study drug.

The Safety Analysis Set will be used for the analysis of safety. Subjects will be analyzed as treated, regardless of the randomized treatment assigned, if this differs from that to which the subject was randomized. Any differences between planned and actual treatment, if any, will be discussed during the blinded review meeting.

Note: if a subject had inadvertently taken the study drug without randomization and/or had negative COVID RT-PCR results post study drug administration, the subject would still be included in the Safety Analysis Set.

Note: FAS and Safety Analysis Set are the same as per definition. To be in line with study protocol, FAS will be used for all efficacy analysis, Safety Analysis Set will be used for all safety analysis (Adverse events, Lab values, Vital Signs, Physical Examination, EKG etc.).

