10.6 Per-Protocol Analysis Set

The Per-Protocol Analysis Set includes all subjects who completed Day 14, took all three doses, and had no important protocol deviations that may affect the primary endpoint of the study.

The exclusion of subjects from the per-protocol analysis set will be discussed and finalized during the blinded review meeting prior to DBL. Protocol deviations that can potentially unblind treatment codes will be reviewed independently by authorized personnel and its impact on population flags will be confirmed prior to DBL.

The PPAS is also used to analyze efficacy endpoints. Demographic and baseline characteristics of the PPAS will also be presented. Subjects will be analyzed according to the treatment group they actually received.

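### The primary efficacy set is grouped by drug received and keeps unrandomised subjects, so no efficacy analysis follows the assigned arm; this matters only if a dosing error occurs

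*SAP*

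**What the plan says.** **Primary efficacy set.** SAP 10.4 reads "All subjects given ≥ 1 dose of study drug will be included in the Full Analysis Set (FAS) according to actual drug received" and makes this set primary for all efficacy endpoints. Its note retains a subject "if a subject had inadvertently taken the study drug without randomization". Protocol 11.3 has the same grouping, "dose of study drug according to actual drug received", as does Protocol 11.1. SAP 10.5 confirms that "FAS and Safety Analysis Set are the same as per definition".

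**Set grouped by assignment.** SAP 10.3 gives its use: "The Randomized Analysis Set will be used for summaries of subject disposition, demographics, baseline characteristics and protocol deviations". Efficacy is not among the uses. The same section adds: "If a subject is randomized but did not take the study drug, then the subject will be included only in the Screened" (and the All-Enrolled and Randomized) sets. Randomised but undosed subjects therefore enter no efficacy analysis.

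**Sensitivity set.** SAP 12.9 repeats the efficacy analyses in the per-protocol set, which "includes all subjects who completed Day 14, took all three doses, and had no important protocol deviations" bearing on the primary endpoint (SAP 10.6). Its grouping rule is "Subjects will be analyzed according to the treatment group they actually received". Protocol 11.1 instead asks for all three doses and evaluability at Day 14, with no deviation criterion. SAP section 13 lists two changes to planned analyses, and neither concerns these definitions.

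**The concern.** Randomisation makes the arms comparable as assigned. Grouping by drug received gives that up for any subject whose product differs from the allocation. Admitting a subject who was never allocated adds someone to whom randomisation does not apply at all. For safety, as-received grouping is usual. For the primary efficacy comparison it lets the reasons behind a dosing error enter the treatment contrast.

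The SAP foresees unrandomised dosing and says that differences between planned and actual treatment will be discussed at the blinded review, but it gives no analytic rule for them. Because the per-protocol set is also grouped by drug received, no planned result shows the comparison as randomised. In a trial of 30 per arm, one subject can decide a result that lies near the threshold.

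**Working it through.** **1. The plan's own figure.** Inputs are 20% vs 5%, one-sided alpha 0.2 and N=54, so 27 per arm (SAP 4.2, Protocol 11.2).

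Power = Φ{[0.15√27 − 0.8416√(2×0.125×0.875)] / √(0.20×0.80 + 0.05×0.95)} = Φ{(0.7794 − 0.3936)/0.4555} = Φ(0.847) = 80.1%.

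The smallest significant difference from 20% is 8.36 points (20% vs 11.64%). Both match the stated ~80% and 8.4 points. At the planned 30 per arm (Protocol 7.1) power is 82.6%. Analysing by assigned arm leaves these planning figures as they are.

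**2. Which sets serve efficacy.**
- FAS: by drug received, unrandomised subjects included.
- Per-protocol set: by drug received.
- Randomized Set: by assignment, no efficacy use.

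If every dosed subject was randomised and received the assigned product, FAS membership and grouping are identical under either rule.

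**3. Illustrative counts (assumed).** Failures a/n₁ on placebo vs b/n₂ on drug, with the planned 20% and 5% read as failure rates. z = (a/n₁ − b/n₂)/√[p̄(1−p̄)(1/n₁+1/n₂)], where p̄ = (a+b)/(n₁+n₂); significant if z ≥ 0.842.

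Example, 6/30 vs 3/30: p̄ = 9/60 = 0.15; SE = √(0.1275×2/30) = 0.0922; z = 0.10/0.0922 = 1.085; p = 0.139.

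| As assigned | One failing placebo-assigned subject counted as drug | One unrandomised failure added on drug |
|---|---|---|
| 6/30 vs 3/30, p=0.139 | 5/29 vs 4/31, p=0.319 | 6/30 vs 4/31, p=0.227 |
| 6/30 vs 2/30, p=0.064 | 5/29 vs 3/31, p=0.195 | 6/30 vs 3/31, p=0.128 |
| 6/30 vs 1/30, p=0.022 | 5/29 vs 2/31, p=0.097 | 6/30 vs 2/31, p=0.059 |

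Only the first row crosses 0.2. If the moved subject in that row is not a failure, 6/29 vs 3/31 gives p=0.116 and nothing crosses. The CMH form, z√[(N−1)/N], alters no crossing; the closest case, 5/29 vs 3/31, becomes p=0.1965.

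**4. Averaged over all outcomes (exact binomial enumeration).** Misdosed subject: a ~ Bin(29, f₀), b ~ Bin(30, f₁), and the subject fails (m=1) with probability g. Compare the call for (a+m)/30 vs b/30 with that for a/29 vs (b+m)/31. Added subject: a ~ Bin(30, f₀), b ~ Bin(30, f₁). Compare a/30 vs b/30 with a/30 vs (b+m)/31. Throughout f₀ = 20%.

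| Event | f₁ | Probability that the call changes | Given that subject fails |
|---|---|---|---|
| One placebo-assigned subject counted as drug | 5% | 3.1% (g=5%) to 5.4% (g=20%) | 17.8% |
| Same | 10% (assumed) | 6.3% (g=10%) to 8.4% (g=20%) | 25.0% |
| One unrandomised drug recipient added | 5% | 0.7% (g=5%) to 2.9% (g=20%) | 14.6% |
| Same | 10% (assumed) | 1.7% (g=10%) to 3.4% (g=20%) | 16.7% |

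The 3.1% splits into significance lost 0.9% and gained 2.2%; the 5.4% into lost 3.6% and gained 1.8%. All figures are conditional on the error having happened, and the documents give no error rate.

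**5. Per-protocol definition.** SAP 11.5 lists death as a reason for early discontinuation, which suggests that a subject who dies before Day 14 has not completed it. SAP 11.17 flags per-protocol subjects whatever their disposition, and SAP 12.9.1.1 counts early discontinuations as failures in an analysis repeated in that set; both allow for non-completers. Completion and evaluability are undefined, so the status of early deaths is open. The share of failures that are deaths before Day 14 is not given, so no size can be put on this.

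**The case against.** The case against acting is substantial. As-received grouping is prespecified in both documents, and SAP 10.5 says the FAS is used for efficacy to stay in line with the protocol. Under planned conduct the effect is nil. Allocation is central, though manual (Protocol 8.12), and an unblinded pharmacist prepares syringes by allocation (Protocol 8.12.1). The blinded review covers subjects not treated as planned (SAP 9.4). Dosing deviations are a recognised category (SAP 12.3), and the sponsor classifies importance (SAP 11.8). A wrongly dosed or unrandomised subject could therefore be left out of the per-protocol set, where received and assigned would then coincide. The crossings in the first row of counts also need a failing subject and a result near the cut-off.

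Most of this stands and limits the weight of the point. It does not remove it. The deviation classification is not guaranteed, review at a meeting is not an analysis rule, and dropping such subjects is not the same as analysing them as randomised.

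A reader might go further and infer that leaving out randomised but undosed subjects is itself an error. It can move a result: 6/30 vs 4/30 (p=0.244) becomes 6/30 vs 3/29 (p=0.151) if one undosed drug-arm failure is dropped. But it is a common choice under blinding. Day 1 is defined by first dosing (Protocol 6.1; Table 5, footnote a), so an undosed subject has no Day 14 as the plan counts it, and an analysis that adds such subjects could rest largely on imputed failures.

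**Conclusion.** The point holds as a contingent weakness that is cheap to remove. No efficacy analysis is planned by assigned arm, and the primary set admits unrandomised subjects. Given one such event, the chance of a changed call at one-sided 0.2 is about 3% to 5% for a placebo-assigned subject counted as drug, and about 0.7% to 2.9% for an added unrandomised drug recipient. These figures rest on 30 per arm, 20% vs 5% read as failure rates, and that subject's failure risk of 5% to 20%. Without such an event the effect on the FAS result is zero.

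Stronger readings are not supported. The protocol and SAP do not contradict each other on the FAS. Neither reports a dosing error, so nothing shows that the primary result is biased. The per-protocol difference affects a sensitivity analysis only; it leaves early deaths undefined but does not show that they are excluded.

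**What to change.** - **SAP 10.4:** define the efficacy FAS as all randomised subjects given at least one dose, analysed by randomised treatment. Place unrandomised dosed subjects in the Safety Set only. Keep as-received grouping for safety and, if wanted, as an efficacy sensitivity analysis.
- **SAP section 13:** record this change. Also list the two SAP 10.6 differences from Protocol 11.1: the Day 14 wording and the added deviation criterion.
- **SAP 10.6 (minor):** state that a subject who took all three doses and died on or before Day 14 is evaluable and counted as a failure.
- **Undosed subjects:** their exclusion need not change. Any supplementary analysis that includes them must count Day 14 from randomisation and report how many outcomes are imputed.
- **Protocol 11.1 and 11.3:** align at the next amendment, since a protocol edit needs ethics approval and regulatory submission first (Protocol 13.2, 13.3).

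The cost is a few sentences in the SAP and an update to the analysis-set flags, which are finalised at the blinded review anyway (SAP 11.1). One more table is needed if the as-received sensitivity analysis is kept. No new assessments are required. If the database is already locked, report the by-assigned-arm result as a labelled supplementary analysis instead.

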10.5 Safety Analysis Set

The Safety Analysis Set includes all subjects who received at least one dose of study drug.

The Safety Analysis Set will be used for the analysis of safety. Subjects will be analyzed as treated, regardless of the randomized treatment assigned, if this differs from that to which the subject was randomized. Any differences between planned and actual treatment, if any, will be discussed during the blinded review meeting.

Note: if a subject had inadvertently taken the study drug without randomization and/or had negative COVID RT-PCR results post study drug administration, the subject would still be included in the Safety Analysis Set.

Note: FAS and Safety Analysis Set are the same as per definition. To be in line with study protocol, FAS will be used for all efficacy analysis, Safety Analysis Set will be used for all safety analysis (Adverse events, Lab values, Vital Signs, Physical Examination, EKG etc.).

10.6 Per-Protocol Analysis Set

The Per-Protocol Analysis Set includes all subjects who completed Day 14, took all three doses, and had no important protocol deviations that may affect the primary endpoint of the study.

The exclusion of subjects from the per-protocol analysis set will be discussed and finalized during the blinded review meeting prior to DBL. Protocol deviations that can potentially unblind treatment codes will be reviewed independently by authorized personnel and its impact on population flags will be confirmed prior to DBL.

The PPAS is also used to analyze efficacy endpoints. Demographic and baseline characteristics of the PPAS will also be presented. Subjects will be analyzed according to the treatment group they actually received.

10.7 PK Analysis Set

The PK Analysis Set will include all subjects in the FAS who have sufficient concentration data to obtain reliable estimates of the key PK parameters and have no important protocol deviations that can influence the validity of the data for the PK endpoints.

PK Analysis Set will be finalized after review of concentration data post DBL and unblinding.

11 Analysis Variables

11.1 Analysis Set Flags

Analysis Set flags will be finalized and authorized by the Study Statistician and Sponsor during blinded review meeting prior to database lock as per definitions provided in Section 10. These flags will be included in the analysis datasets.

11.2 Treatment groups

All analyses will be summarized by treatment group. The following treatment groups will be defined in the analysis datasets.

- rhu-pGSN
- Placebo

11.3 Analysis Visits

All analysis datasets with measurements taken at more than one visit/time point will have analysis visit and timepoint as defined below.

Visit as in CRF	Visit Representation in summaries
Screening	-
-	Baseline

Visit as in CRF	Visit Representation in summaries
Day 1	Day 1
Day 2	Day 2
Day 3	Day 3
Day 7	Day 7
Day 14	Day 14
Day 28	Day 28
Day 60	Day 60
End of Study / Early Termination	Early Termination
End of Study / Early Termination	End of Study

The End of Study and Early Termination visits will be presented separately. Screening Visit will be summarized only in listings except for the demographic and baseline characteristics data.

A subject is considered to have attended any visit only if at least one assessment has been taken at the visit.

11.3.1 Timepoints

Vital signs and PK Samples will be collected at various timepoints, these will be included for summaries as follows:

Endpoints	Timepoint in Analysis
Vital Signs	Dose X, Pre-Dose Dose X, End of Study Drug Administration Dose X, 30 Minutes Post-Dose
Plasma concentration	Pre-Dose 1 Hour Post-Dose X Hours Post-Dose

11.3.2 Study Period

Study Periods will be assigned as follows:

- Informed Consent Date to the day before first IMP date – ‘Screening’
- Date of first IMP to Day 14 – ‘Treatment Period’
- Day 15 to End of Study – ‘Follow-up Period’

11.3.3 Visit Imputation

For assessments where shift summaries are required (WHO Severity Score and CURB-65 Score), records will be imputed for all subjects in Safety Analysis Set in all scheduled visits and marked as ‘Missing / Not Done’ if either the subjects did not attend the visit or discontinued or had missing assessment at the respective visit.

11.3.4 Repeat Assessments

If there are any repeat assessments, they will be logged as unscheduled visits and the reason for unscheduled visit will be marked as repeat assessment. In such cases, these unscheduled visits will be mapped to the visit for which repeat assessment was taken. In case of multiple repeat assessments on the same day, the latest assessment will be considered for analysis.

For WHO Severity scores, if there are more than one repeat assessments on the same day, then highest non-missing score will be considered for analysis.

11.4 Study Duration

Study Duration (days) = (Date of Last Visit –First IMP Date) + 1.

11.5 Discontinued Subjects

Discontinued subjects will have safety assessments taken at Early Withdrawal visits. These will be presented separately and will not be combined with EOS if results are available.

The reason for discontinuation from the study will be mapped in the analysis as follows:

Primary reason for early discontinuation (As in CRF)	Reason for early termination from the study
Subject withdrew consent	Subject withdrew consent
Unacceptable AE	Unacceptable AE
Pregnancy	Pregnancy
Subject is unwilling or unable to continue the study or is lost to follow up	Subject unwilling / lost to follow-up
Subject is non-compliant with study procedures/study protocol	Protocol Deviation
Investigator decides that withdrawal from the study is in the best interest of the subject	At the discretion of the Investigator
Any clinically significant change in subject's medical condition (at the discretion of the Investigator)	At the discretion of the Investigator due to change in medical condition
Treatment unblinded	Treatment Unblinded
Sponsor decision to end the study	Sponsor decision to end the study
Death	Death
Other	Other

11.6 Replacement Subjects

If one of the eligible subjects is included in the study as replacement, then the subject will be flagged as replacement subject with subject ID of the replaced subject. For example, if subject XXXY is replaced, then replacement subject XXXX will be flagged as 'Replacement for XXXY'. These flags will be used only in listings, and not in any analyses. Summaries will include data for replacement subjects like any other subject in that treatment group.

11.6.1 Common Derivations

The following variables will be derived in analyses datasets and used in summaries as per the formula below:

- BMI (kg/m²) = Weight in kg / (Height in cm x 0.01)². Height from screening, and weight from respective visit will be used.
- Age (years) = ((Date of Informed consent – Date of Birth) + 1)/365.25
- QTcF (msec) = QT (msec) / (RR (msec)/1000)^{1/3}
- Duration (days) = (End Date – Start Date) + 1
- Start Day (days) = (Start Date – First IMP date) + 1

These variables will be derived and verified against EDC calculated values, if available. In cases where they do not match, queries will be raised. If not reconciled until database lock, derived values will be considered correct and will be used for analysis.

